5.5.1.2 Change from Baseline using the NRS-11

If ≥4 of the 7 NRS-11 readings associated with a single visit are missing, then the score for that visit will be treated as missing. If <4 readings are missing, the value associated with a visit will be the average of the non-missing readings.

A sensitivity analysis, similar to that described for PedsQL in Section 5.5.1.1, will be performed to assess the impact of MNAR data on the NRS-11 results. The imputation described in Section 5.5.1.1 will be performed for missing NRS-11 data, and the sensitivity analysis will be performed as detailed in Section 6.11.2.3.

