4.1.2.2.2 Numerical Rating Scale=11 (NRS-11)

The NRS-11 is a self-report segmented 11-point numeric scale that assesses pain severity over the past 24 hours. The NRS-11 is administered daily over 7 consecutive days, inclusive of the study visit day, during the Treatment Phase as described in the SoA (Sections 1.3-1.4 of the protocol). For the ET visit, the assessment is only conducted once at the site and not for the preceding 6 days. Participants ≥ 8 years of age are administered the NRS-11 as a self-report.

Participants are asked to select the one number from 0 to 10 that best describes their worst pain over the past 24 hours for target tumor pain with 0 representing "no pain" and 10 representing "worst pain you can imagine". The NRS-11 score presented each visit will be taken as the average of the responses over the 7 consecutive days leading up to and including the visit day, with no transformation applied. The scale is presented in Appendix 1.3.

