5.5.1.3 Change from Baseline using the PII

If >3 of the 6 PII questions associated with a single assessment are missing, then the score for that assessment will be treated as missing. Otherwise, the score for a given assessment will be taken as the average of the non-missing assessment scores. If ≥4 of the 7 PII assessments corresponding to a single visit are missing, then the score for that visit will be treated as missing. Otherwise, the value associated with a visit will be the average of the non-missing readings.

A similar sensitivity analysis will also be performed to assess the impact of MNAR data on the PII results. The imputation described in Section 5.5.1.1 will be performed for missing PII data, and the sensitivity analysis will be performed as detailed in Section 6.11.2.3.

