6.10 PRO Compliance & Completion

Compliance and completion rates will be provided for the PRO instruments corresponding to the secondary endpoints of PedsQL, NRS-11, and PII.

Compliance rate is calculated as participants with minimum requirements for scoring divided by the number of participants with PRO assessments expected. For compliance rates, the summaries will include reasons for missing observations among patients who were expected to complete the questionnaire by assessment.

For completion rate, this will be derived in a similar manner as the compliance rate, however the subset of the FAS who are considered eligible to complete each questionnaire, as per Table 14, is used as a fixed denominator. For completion rates, the summaries will include reasons for missing observations among the eligible participants within the eligible FAS population by assessment. Reasons for missing observations include, but are not limited to, progression, adverse event, subject withdrawal, lost to follow-up, patient or physician decision, patient was too ill to complete, not completed due to site staff error, technical problems with eDiary, patient non-compliance, etc.

Document: S:\Q_146\Q_03974\MEK-NF-201\Prog_Stat\Documentation\SAP\MEK-NF-201 SAP v1.0.0.docx

Author:

Table 14: PRO Age Range Eligibility

PROs	Ped	dsQL	NRS-11		PII
Age of Participant (years)	Self-report	Parent Proxy	Self-Report	Self-report	Parent Proxy
2		Х			
3		Х			
4		Х			
5	Х	Х			
6	Х	Х		Х	Х
7	Х	Х		Х	Х
8-17	Х	Х	Х	Х	Х
≥18	Х	Ха	Х	Х	

a If a participant is ≥ 18 years of age, but in the opinion of the investigator has cognitive deficiencies that would inhibit accurate collection of PRO data, a parent or legal guardian must also complete the appropriate parent-proxy PRO.

For the diary instruments where more than one day was expected (NRS-11 and PII), the number and percent of participants with ≥1 complete diary day, ≥2 complete diary days, ≥3 complete diary days, etc. for the diary periods associated with the study visits will also be provided.

All summaries of compliance/completion will be displayed with the relevant PROs.

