An MMRM will be fitted separately by age cohort and questionnaire type for each PedsQL score listed in Section 4.1.2.2.1. Change from baseline in PedsQL score will be the dependent variable, visit will be fitted as a fixed effect, and baseline PedsQL score used as a covariate. Covariance structures will be trialed in the order of decreasing complexity, with the first structure that converges without error used. The structures tested are as follows: Unstructured, Heterogenous Toeplitz, Heterogenous Autoregressive, Autoregressive, Heterogenous Compound Symmetry, Compound Symmetry, Variance Components. A Kenward-Roger approximation will be used for the degrees of freedom. This model will be fitted twice, once using only data through Cycle 13, and once including data from the entire study (timepoints with < 5 subjects will not be presented). EOT and unscheduled visits will be mapped to the closest scheduled tumor visit following the rules outlined in Table 13, and will only be included in the model if the participant has no other record at that timepoint. For the MMRM change from baseline tables, the least square (LS) Means estimates will be presented with associated standard errors, 95% Cls and p-values by visit. Plots of the LS Means estimates over time with associated 95% Cl bands will be presented separately by age cohort and questionnaire type for both models.

Box and whiskers plots of change from baseline in total score will be presented by visit and confirmed objective response status for the adult cohort, pediatric cohort self-report, and pediatric cohort parent proxy separately.

A waterfall plot of change from baseline will be presented by visit for adult cohort, pediatric cohort self-report and pediatric cohort parent proxy separately for each PedsQL domain at Cycles 5 and 13 with a line representing the respective within-patient meaningful change threshold derived by anchor-based analysis. This plot will be color-coded by confirmed objective response status.

Additionally, a sensitivity analysis will be performed for each PedsQL score using the imputed data described in Section 5.5.1.1. The MMRM analysis described above will be performed with data up to Cycle 13. LS Means estimates, associated standard errors, 95% Cls and p-values will be presented by visit.

Document: S:\Q_146\Q_03974\MEK-NF-201\Prog_Stat\Documentation\SAP\MEK-NF-201 SAP v1.0.0.docx

Author:

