An MMRM will be fit separately by age cohort with change from baseline in NRS-11 score as the dependent variable, visit as a fixed effect and baseline NRS-11 score as a covariate. The covariance structure will be decided in the manner described in Section 6.11.2.2, and a Kenward-Roger approximation will be used for the degrees of freedom. This model will be fitted twice, once using only data through Cycle 13, and once through Cycle 24. EOT visits will be mapped to the closest scheduled tumor visit following the rules outlined in Table 13, and will only be included in the model if the participant has no other record at that timepoint. LS Means estimates will be presented with associated standard errors, 95% Cls and p-values by visit. Plots of the LS Means estimates over time with associated 95% Cl bands will be presented separately by age cohort for both models.

Box and whiskers plots of change from baseline will be presented by visit and confirmed objective response status for each age cohort separately.

A waterfall plot of change from baseline in NRS-11 will be presented by visit for adult cohort, pediatric cohort self-report and pediatric cohort parent proxy separately at Cycles 5 and 13, with a line representing the respective within-patient meaningful change threshold derived by anchorbased analysis. This plot will be color-coded by confirmed objective response status.

Document: S:\Q_146\Q_03974\MEK-NF-201\Prog_Stat\Documentation\SAP\MEK-NF-201 SAP v1.0.0.docx
Author:

Additionally, a sensitivity analysis will be performed on the NRS-11 results using the imputed data described in Section 5.5.1.2. The MMRM analysis described above will be performed with data up to Cycle 13. LS Means estimates, associated standard errors, 95% Cls and p-values will be presented by visit.

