An MMRM will be fit separately by age cohort and questionnaire type, with change from baseline in PII score as the dependent variable, visit as a fixed effect and baseline PII score as a covariate. The covariance structure will be decided in the manner described in Section 6.11.2.2, and a Kenward-Roger approximation will be used for the degrees of freedom. This model will be fitted twice, once using only data through Cycle 13, and once through Cycle 24. Unscheduled and ET visits will be mapped to the closest scheduled tumor visit following the rules outlined in Table 13, and will only be included in the model if the participant has no other record at that timepoint. LS Means estimates will be presented with associated standard errors, 95% CIs and p-values by visit. Plots of the LS Means estimates over time with associated 95% CI bands will be presented separately by age cohort and questionnaire type for both models.

Box and whiskers plots of change from baseline will be presented by visit for adult cohort, pediatric cohort self-report and pediatric cohort parent proxy separately.

Document: S:\Q_146\Q_03974\MEK-NF-201\Prog_Stat\Documentation\SAP\MEK-NF-201 SAP v1.0.0.docx

Author:

A waterfall plot of change from baseline in PII will be presented by visit for adult cohort, pediatric cohort self-report and pediatric cohort parent proxy separately at cycles 5 and 13, with a line representing the respective within-patient meaningful change threshold derived by anchor-based analysis. This plot will be color-coded by confirmed objective response status.

Additionally, a sensitivity analysis will be performed on the PII results using the imputed data described in Section 5.5.1.2. The MMRM analysis described above will be performed with data up to Cycle 13. LS Means estimates, associated standard errors, 95% Cls and p-values will be presented by visit.

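### The 4-of-7 diary rule voids the one-reading ET score that the PII model is told to use, and the PRO windowing rule, read literally, labels off-drug Safety Follow-Up scores as on-treatment visits

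*SAP*

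**What the plan says.** **Scoring.** NRS-11 and PII visit scores are averages over seven consecutive days ending on the visit day (SAP 4.1.2.2.2 and 4.1.2.2.3). The PII score for a visit is missing under this condition: "If ≥4 of the 7 PII assessments corresponding to a single visit are missing" (SAP 5.5.1.3). The NRS-11 condition is the same: "≥4 of the 7 NRS-11 readings associated with a single visit are missing" (SAP 5.5.1.2). Neither section has an exception for any visit.

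**ET.** For both instruments the SAP says: "For the ET visit, the assessment is only conducted once at the site and not for the preceding 6 days". Protocol 8.1.2.1 and 8.1.2.2 agree.

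**Models.**
- PII (SAP 6.11.2.3.2): "Unscheduled and ET visits will be mapped to the closest scheduled tumor visit following the rules outlined in Table 13", and such a record "will only be included in the model if the participant has no other record at that timepoint".
- NRS-11 (SAP 6.11.2.3.1): "EOT visits will be mapped to the closest scheduled tumor visit following the rules outlined in Table 13". ET is not named.
- PedsQL (SAP 6.11.2.2): "EOT and unscheduled visits will be mapped to the closest scheduled tumor visit following the rules outlined in Table 13".

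EOT is a long-term follow-up visit (SAP 2.2, Table 4). In that phase only the P-OMAQ and PedsQL are collected (protocol 8.1.2).

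**Windowing.** SAP 5.6 keeps the nominal visit for a PRO record if it is C1D1 or listed in Table 13. Every other record is assigned by study day through Table 13, and a valid nominal reading at the target visit takes precedence. Safety Follow-Up is not in Table 13, and no PRO rule excludes it.

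**Safety Follow-Up.** Early stoppers must attend both ET and a Safety Follow-Up visit 30 (+5) days after the last dose (protocol 7.1). PedsQL, NRS-11 and PII are all collected there, the last two with a full seven-day diary (protocol Table 7). SAP Table 3 gives the visit its own label, SFU, for all outputs.

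**The concern.** Three rules do not fit together. The PII model is told to accept ET scores, but the PII scoring rule leaves none to accept. The NRS-11 model is told to map a visit that cannot hold NRS-11 data, while the visit that does hold it goes unnamed. A visit about a month off drug has a complete diary, passes the scoring rule, and under the general windowing rule can be relabelled as an on-treatment cycle.

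Change in pain and quality of life are secondary endpoints, and SAP 5.8 fixes Cycle 13 as the PRO time point. For someone who stops shortly before Cycle 13, the reading nearest the last dose could be discarded and an off-drug score reported as Cycle 13. Two programmers working from the same SAP could build different data sets for the by-visit summaries, the mixed models and the missing-not-at-random sensitivity analysis.

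**Working it through.** There is no plan figure to reproduce. The check is a count of readings and a walk through the Table 13 windows.

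**1. ET against the 4-of-7 rule.**
- Readings at ET: 1 (SAP 4.1.2.2.2, 4.1.2.2.3).
- Missing out of 7: 7 − 1 = 6. The rule voids the score at 4 or more missing, so it tolerates at most 3.
- 6 ≥ 4, so every ET diary score is missing as the rule stands. The ET provision in the PII model can then never add a score.

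For NRS-11 the model text does not name ET. An ET reading could reach that model only through the general rule in SAP 5.6, and SAP 5.5.1.2 would void it first.

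**2. Where Safety Follow-Up lands.** Inputs from Table 13: Cycle 9 covers days 212–294 (visit day 239), and Cycle 13 covers days 295–406 (visit day 351). Let s be the study day of the last dose, from 1 to 350, that is, before the Cycle 13 visit. Safety Follow-Up is on day s + 30 to s + 35. It falls in the Cycle 13 window when 295 ≤ s + lag ≤ 406.
- Lag 30: s = 265 to 350, which is 86 days; 86/350 = 24.6%.
- Lag 35: s = 260 to 350, which is 91 days; 91/350 = 26.0%.

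The diary runs from six days before the visit to the visit day. Entries therefore date from 24–30 days after the last dose (visit at +30) or 29–35 days (visit at +35).

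**3. Where ET lands, assuming it is held on the last-dose day.**
- s = 295 to 350 (56 days; 56/350 = 16.0%): ET and Safety Follow-Up both fall in the Cycle 13 window. ET fails the 4-of-7 rule, while a complete Safety Follow-Up diary (7 of 7) passes.
- s = 265 to 294 (30 days) or 260 to 294 (35 days): ET falls in the Cycle 9 window, where a valid day-239 reading takes precedence. Only Safety Follow-Up reaches Cycle 13.

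**4. Sensitivity of the counts.**
- Cycle 13 visit at day 346 (−5 days): 81 to 86 of 345 days; competing days 51.
- Cycle 13 visit at day 356 (+5 days): 91 to 96 of 355 days; competing days 61. Across both shifts the shares are 23–27% in total and 15–17% competing.
- Dosing days only (days 1–21 of each cycle): 65 to 70 of 266 (24–26%); competing days 42.
- ET held 14 days after the last dose: competing days become s = 281 to 350, which is 70 days (70/350 = 20.0%).

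**5. Effect on the sensitivity analysis.** SAP 5.5.1.1 to 5.5.1.3 set monotone-missing scores to baseline, and the model is refitted through Cycle 13. If ET is void and Safety Follow-Up is not mapped, an early stopper's Cycle 13 score is monotone missing and becomes the baseline value. If Safety Follow-Up is mapped, the off-drug score fills that place.

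**The case against.** **The six other ET readings were never scheduled, so they are not missing.** SAP 6.10 counts diary days under this limit: "For the diary instruments where more than one day was expected (NRS-11 and PII". That is a sensible reading and may be what was meant. But it sits in the compliance section. The scoring rules count out of seven without condition and do not adopt it.

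**Safety Follow-Up was never meant to be mapped.** Much of the specific text supports this: the SFU label in SAP Table 3, the absence of the visit from all three model lists, and protocol Table 1, which limits the pain endpoint to the Treatment Phase. Against that, SAP Table 1 drops the limit, the Safety Follow-Up column sits in the Treatment Phase schedule, and the catch-all in SAP 5.6 has no exclusion. Intent leans towards exclusion, but the operative windowing rule says otherwise.

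**The sensitivity analysis already covers early stoppers.** This stands in part. Setting monotone-missing scores to baseline tests a no-improvement assumption for voided ET scores. Its input still depends on the unresolved Safety Follow-Up question.

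**The contradiction does not extend to every PRO.** Correct. The direct clash between scoring rule and model is for PII only. For NRS-11 the fault is a visit name that cannot supply data. PedsQL is one form per visit, so the 4-of-7 rule does not touch it, and EOT is properly named there because PedsQL is collected at that visit. A reader might also object that SAP 5.6 lacks a rule for two mapped PedsQL records in one window. That is missing detail, and a multiple-record averaging rule for other efficacy assessments follows nearby.

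**Conclusion.** The PII conflict is an error in the text: SAP 5.5.1.3 removes every score that SAP 6.11.2.3.2 provides for at ET. Naming EOT in the NRS-11 model is also wrong on the documents. The Safety Follow-Up point is a conflict between a literal general rule and more specific text, which the SAP should resolve.

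A reader might infer that about a quarter of participants would carry an off-drug Cycle 13 score. The documents do not support that. The 86 to 91 of 350, and the 56 competing days, count possible last-dose days. They assume nominal visit days, ET on the last-dose day (for the 56) and no scheduled visit after the last dose. The plan gives no number of early stoppers or pattern of stopping times, so neither the number affected nor any bias can be computed. Nor can one say that off-drug scores will enter the models; the SAP permits that reading and does not state that it will be followed.

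The reach is limited. Only early stoppers or people with missed visits are affected, scheduled scores stay in the models, and the primary response endpoint is untouched. The meaningful-change addendum (SAP 5.8) is not among the documents and may settle visit assignment for its own counts, so the point concerns the mixed models and by-visit summaries. The SAP should be corrected, with medium confidence about how much it matters in practice.

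**What to change.** - **Reconcile SAP 5.5.1.2 and 5.5.1.3 with 6.11.2.3.2.** Either state that the single ET reading is the ET score and is exempt from the 4-of-7 rule, or remove ET from the diary-score models. The first keeps the reading nearest the last dose but puts a noisier one-day score among seven-day means. The second avoids that and loses the reading. Either resolves the conflict.
- **Correct the NRS-11 model text in 6.11.2.3.1.** If ET is kept, change EOT to ET; otherwise delete EOT.
- **Add a sentence to SAP 5.6** that Safety Follow-Up PROs are not mapped through Table 13 and are summarised under the SFU label. Without it, a mapped Safety Follow-Up score could still displace an exempted ET score through the no-other-record condition. The cost is that some early stoppers will have no Cycle 13 score.

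These are a few sentences of SAP wording, with no new data and no new analyses.

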5.5.1.3 Change from Baseline using the PII

If >3 of the 6 PII questions associated with a single assessment are missing, then the score for that assessment will be treated as missing. Otherwise, the score for a given assessment will be taken as the average of the non-missing assessment scores. If ≥4 of the 7 PII assessments corresponding to a single visit are missing, then the score for that visit will be treated as missing. Otherwise, the value associated with a visit will be the average of the non-missing readings.

A similar sensitivity analysis will also be performed to assess the impact of MNAR data on the PII results. The imputation described in Section 5.5.1.1 will be performed for missing PII data, and the sensitivity analysis will be performed as detailed in Section 6.11.2.3.

5.5.2 Other Endpoints

5.5.2.1 Adverse Events

Missing and/or incomplete dates/times for AEs are imputed in a manner resulting in the earliest onset or the longest duration during the treatment period, taking additionally into account that the

Document: S:\Q_146\Q_03974\MEK-NF-201\Prog_Stat\Documentation\SAP\MEK-NF-201 SAP v1.0.0.docx
Author:

Protocol Number: MEK-NF-201

start date/time should not be after the stop date/time. Stop dates/times will not be imputed if the AE is ongoing. To do this, it is necessary to define the earliest and latest possible date for an event, which is done as follows:

The earliest possible date is derived as:

- The date itself if it is complete.
- The date of the first day of the month, if month and year are available but day is missing.
- The date of the first day of the year, if year is available but day and month are missing.
- A very early date, e.g., 01JAN1900 if the date is completely missing.

The latest possible date is derived as:

- The date itself if it is complete.
- The date of the last day of the month, if month and year are available but day is missing.
- The date of the last day of the year, if year is available but day and month are missing.
- A very late date, e.g., 31DEC2100 if the date is completely missing.

These earliest/latest possible dates are used to impute the missing/incomplete start/stop dates.

Missing/incomplete start dates will be imputed according to the following:

- 1. If the earliest possible start date is on or after the start of treatment administration:
 - The earliest possible start date.
- If the earliest possible start date is before the start of treatment administration, the minimum of:
 - The date of first study treatment administration.
 - The latest possible start date.
 - The latest possible stop date.

Missing/incomplete stop dates will be imputed according to the following:

- 1. If the latest possible stop date is before the end of treatment administration:
 - The latest possible stop date.
- If the latest possible stop date/time is after the end of treatment administration, the maximum of:
 - The date of final study treatment administration
 - The earliest possible stop date
 - The earliest possible start date

The imputation method will only be used to determine the time of the event relative to the first administration of study treatment.

In the occasion of missing severity data for an AE, no imputation will be performed, and severity will be presented as "Missing" in summary tables.

In the event that no coding information is available for a specific AE, the AE will be presented as an 'Uncodable Event' in summary tables.

Document: S:\Q_146\Q_03974\MEK-NF-201\Prog_Stat\Documentation\SAP\MEK-NF-201 SAP v1.0.0.docx

Author:

5.5.2.2 Demographics

For determining age when the date of birth is not known completely, a missing day only will be imputed as the 15th, a missing day and month will be imputed as the 2nd of July which is day 183 in the year.

